8.1.2 AIM 2 (SECONDARY) OUTCOME POWER

AIM 2: Improvement in depressive symptoms. Our Aim 2 outcome is a reduction in depressive symptoms from the study qualifying PHQ score to follow-up PHQ score documented as part of routine clinical care 3-13 months later.

Power calculations for Aim 2 estimate Minimal detectable difference (MDDs) that could be observed with 80% power, assuming a two-sided type 1 error rate of 0.05, under different scenarios regarding engagement (ranging from 30-50%). These calculations assume a 60% PHQ follow-up rate (among the initial sample of 800 patients) and standard deviation of 6.7 for the outcome, based on preliminary data from both study sites. Similar to Aim 1, the analysis for Aim 2 will adjust for the baseline value of the outcome (and potentially other baseline covariates). MDDs are also computed for a range of R² related to these prognostic variables, ranging from R² of 0 (corresponding to no prognostic covariates) to 0.4 (corresponding to more highly prognostic covariates). For engagement rates of at least 35%, or for lower engagement rates combined with highly prognostic baseline characteristics, the study sample size of 800 has sufficient power to detect a clinically meaningful difference of at least 5 for the outcome of change in PHQ, between baseline and intervention patients (and smaller in some scenarios). A prior study found a change between 2.59-4.78 to be the minimal clinically important difference (MCID), leading to a commonly defined threshold of 3-5 points for the MCID.

Table 8.1.2. Minimal detectable difference (MDD) in change in PHQ score, from baseline to follow-up, with 80% power comparing intervention versus control patients (intention-to-treat [ITT] analysis); and corresponding difference among engaged patients, across levels of engagement from 30-50%. MDDs are presented under different values of the R² of the included baseline covariates (e.g., baseline value of the outcome).

R ² of baseline	Mean change in in PHQ score, from baseline to follow-up						
covariate	ITT	Engaged patients (%) versus usual care					
		30%	35%	40%	45%	50%	
0	1.72	5.73	4.91	4.30	3.82	3.44	
0.1	1.62	5.40	4.63	4.05	3.60	3.24	
0.2	1.54	5.13	4.40	3.85	3.42	3.08	
0.3	1.44	4.80	4.11	3.60	3.20	3.08	
0.4	1.32	4.40	3.77	3.30	2.93	2.64	

8.2 POPULATIONS FOR ANALYSIS

Main analyses will be conducted following an intention-to-treat approach, including all individuals randomly selected to be offered the intervention (regardless of their engagement with or exposure to the intervention), as well as all patients not randomly selected to be offered the intervention (usual care controls), under the Zelen design.

8.3 STATISTICAL ANALYSES

8.3.1 ANALYSIS OF THE PRIMARY OUTCOME

The primary outcome is a continuous measure of days of OUD treatment with buprenorphine in the 365 days after randomization. We will use a linear regression analysis adjusted for the baseline value of the outcome, health system, and other pre-specified covariates measured pre-randomization (i.e., analysis of covariance [ANCOVA]). From the regression model we will estimate the mean difference in days of OUD treatment comparing patients randomly selected to be offered the CC intervention vs. the usual primary care control arm. Standard errors will be calculated using the robust (sandwich) variance estimator⁴² given the non-normally distributed outcome (see Supplement 3, part A). Unless otherwise specified, all analyses will follow intention-to-treat principles with individuals analyzed according to the randomized intervention group.

Adjusting for baseline variables associated with the outcome can improve precision of intervention effect estimates and power of statistical tests. ^{43, 44} To determine the set of baseline variables that will be

adjusted for (in addition to health system and the baseline value of the outcome), we plan to use secondary data from before the start of the trial to conduct simulations to identify which covariates are associated with days of OUD treatment (measured in preliminary data) and to explore the impact of adjustment for such covariates on precision and power.⁴⁵ We reiterate that no post-randomization data will be used for covariate selection. The full details of the simulation-based approach and the variables selected for adjustment in the primary analysis will be pre-specified in the standalone statistical analysis plan (SAP) for the trial.

8.3.2 ANALYSIS OF THE SECONDARY DEPRESSIVE SYMPTOM OUTCOME

The powered secondary outcome is the change in PHQ score from baseline to follow-up (in the period 3-13 months after randomization). Following a similar approach as for the primary outcome, we will use a linear regression analysis of the change score (follow-up score minus baseline score), adjusted for the baseline score, health system, and other pre-specified covariates measured pre-randomization. From the regression model we will estimate the mean difference in the PHQ change score comparing patients randomly selected to be offered the CC intervention vs. the usual primary care control arm. Standard errors will be calculated using the robust (sandwich) variance estimator. The set of baseline variables that will be adjusted for will be selected using a parallel approach as for the primary outcome, prespecified in the standalone SAP.

Based on preliminary data, we expect that a subset of patients will have more than one follow-up PHQ (either PHQ-2 or PHQ-9) documented within the follow-up window. To determine our final approach to identifying which of these follow-up scores will be used, our biostatistical team will be conducting simulations to identify the most powerful analytic approach (from among all options considered that yield unbiased intervention effect estimates and correct type 1 error rates) using data from before randomization. Options that will be considered include selecting a single follow-up score (e.g., score documented closest to 12 months) and using all scores within the follow-up window and accounting for correlation of repeated measures within an individual. Additional details on the general simulation approach are provided in Supplement 3, part B, with full details and the final analytic approach to be specified in the standalone statistical analysis plan (SAP) for the trial.

8.3.3 OTHER SECONDARY ANALYSES

Analyses of secondary outcome measures will follow the same general analysis approach as the primary outcome, applying a generalized linear model with appropriate outcome distribution and link function, and using a robust (sandwich) variance estimator. Secondary outcomes that are continuous measures (e.g., days of any medication treatment for OUD) will be analyzed using a parallel approach as for the primary and powered secondary outcome analyses. Models will adjust for health system and for the baseline value of outcome measures (if available), using the continuous version of binary measures where available (e.g., for clinically significant improvement in depressive symptoms we plan to adjust for the baseline PHQ score). Other pre-selected covariates to be adjusted for in the models will be identified using a similar approach as for the primary outcome, pre-specified in the standalone SAP. For binary

secondary outcomes (e.g., sustained buprenorphine treatment for OUD, clinically significant improvement in depressive symptoms), we plan to use a modified Poisson regression with robust variance to estimate a relative rate. For the secondary composite measure of any major adverse event (including opioid OD, other drug OD, suicide attempt or other self-harm, hospitalizations, or death) during the follow-up period, we will apply survival analysis methods for time-to-event data (i.e., time to the first major adverse event). Patients are censored at 12 months (end of follow-up) or disenrollment from the health system (for one of the sites with enrollment information available). Kaplan-Meier curves will be generated and Cox proportional hazards models stratified by health system will be used to estimate hazard ratios. In addition, we may also consider covariate-adjusted estimators for time-to-event outcomes that can improve precision and power⁴⁵, such as the targeted minimum loss-based estimator of the difference in restricted mean survival times (RMSTs) at 12 months between intervention and control groups. The final analytic approach will be specified in the standalone SAP for the trial.

8.3.3.1 EXPLANATORY MODERATION ANALYSES

The effect of the intervention on each of the main trial outcomes could be modified by the other main outcome. To address this question, we plan to explore whether, for patients with larger reductions in depressive symptoms, there is a stronger effect of the intervention on days of OUD treatment, as compared to patients with smaller reductions in depressive symptoms; and similarly, whether patients with more days of OUD medication treatment show a stronger effect of the intervention on reductions in depressive symptoms over the study follow-up as compared to patients with fewer days of OUD medication treatment.

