3 OBJECTIVES AND OUTCOMES

3.1 OBJECTIVES

The MI-CARE trial evaluates the effectiveness of an offer of 12 months of CC to primary care patients with evidence of depression and OUD compared to usual primary care. The MI-CARE intervention is designed to support "whole health" by engaging patients in medication treatment for OUD and depression, reducing depressive symptoms, and addressing common comorbid conditions that complicate OUD and depression (e.g., anxiety, pain, sleep, and other mental health and substance use disorders).

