3.2.2 SECONDARY TRIAL OUTCOME - POWERED DEPRESSION OUTCOME

AIM 2: Improvement in depressive symptoms. A reduction in depressive symptoms from the study qualifying PHQ score to follow-up PHQ score documented as part of routine clinical care 3-13 months later.

The analytical approach to handling the situation in which some individuals have multiple PHQ measures documented during the follow-up window will be specified in the statistical analysis plan (a brief overview of the methods considered and the general simulation approach to guide the choice of method is given in Supplement 3, part B).

Rationale: A prior study found a change between 2.59 and 4.78 to be the minimal clinically important difference (MCID), leading to a commonly defined threshold of 3-5 points for the MCID. However, no studies have evaluated the PHQ in patients with OUD. Therefore, we chose to not pre-define a specified threshold. In addition, we use the interval of 3-13 months to ensure 60% follow-up PHQ-9s based on preliminary studies showing that 13 months after randomization maximizes follow-up (likely due to EHR prompts at 12 months for repeat screening). (See Supplement 2 for additional rationale).

To get a fuller picture of changes in depressive symptoms we will also assess clinically significant improvement in depressive symptoms defined as at least a 50% decrease in PHQ score.

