3.3.2 COVARIATES

The sample will include important subgroups of patients who may respond differently to the intervention and for whom different outcomes are most relevant. Outcomes will therefore secondarily be described in important subgroups at baseline (defined as up to 2 years before randomization), including the following:

- Demographics of study population at baseline. Used to describe baseline characteristics of the sample (e.g., age, sex, race, ethnicity, zip code-based neighborhood characteristics such as SES and type of insurance).
- **Diagnoses of medical conditions and clinical comorbidity at baseline.** Used for stratified analyses and to explore whether these characteristics modify the reach or effectiveness of the intervention.
- **Substance use-related and pain comorbidity at baseline**. Used for stratified analyses and to explore whether these characteristics modify the reach or effectiveness of the intervention.
- OUD medication treatment at baseline. These groups will be used for stratified analyses, to
 explore whether these characteristics modify the reach or effectiveness of the intervention, and
 for subgroup analyses.
- **Mental health subgroups at baseline**. We will evaluate sub-groups based on mental health comorbidity to explore whether the intervention has differential reach (engagement and OUD treatment) or effectiveness across subgroups (e.g., serious mental illness, ADHD, PTSD).
- *Healthcare utilization at baseline* (e.g., primary care, mental health, addiction specialty, ED, and hospital utilization, etc.). Used for stratified analyses and to explore whether these characteristics modify the reach or effectiveness of the intervention.

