8.1.1 AIM 1 (PRIMARY) OUTCOME POWER

With a sample size of 760 patients (assuming 5% of the target 800 are missing outcome data, e.g., due to leaving the state) we will have 80% power to detect a difference in the mean number of days of OUD treatment (primary outcome) of 20 days under a two-sided type 1 error rate of 0.05, assuming a standard deviation (SD) of 98.3 (based on preliminary data). Because we expect that half or more of patients randomized to the trial intervention arm will not agree to participate in the intervention, this incremental benefit is attenuated by those not getting the intervention for whom we expect similar treatment and response to treatment as usual care (mean number of days of 46.7); see **Table 8.1.1**. For example, if 35% of patients engage with the intervention, to have 80% power we would need to observe a mean difference of 57.1 days of OUD treatment comparing engaged patients versus usual care patients (e.g., from 46.7 to 103.8 days), whereas if 50% engage we would need to observe a mean difference of 40 days (from 46.7 to 86.7 days). In these calculations, information on the mean and SD of the outcome was estimated using preliminary data from one of the two sites (the other site did not have preliminary data available on the primary outcome at the time of Protocol development).

Table 8.1.1. Minimal detectable difference (MDD) in the mean number of days of OUD treatment with 80% power comparing intervention versus control patients (intention-to-treat [ITT] analysis); and corresponding difference among engaged patients, across levels of engagement from 30-50%. MDDs are presented under different values of the R² of the included baseline covariates (e.g., baseline value of the outcome).

R ² of baseline covariate	paseline covariate Mean change in days of OUD treatment					
	ITT	Engaged patients (%) versus usual care				
		30%	35%	40%	45%	50%
0	20	66.7	57.1	50.0	44.4	40.0
0.1	19	63.3	54.2	47.5	42.2	38.0
0.2	17.9	59.7	51.1	44.8	39.8	35.8
0.3	16.7	55.8	47.8	41.9	37.2	33.5
0.4	15.5	51.7	44.3	38.8	34.4	31.0

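### Section 8.3.3.1 uses each main outcome as a moderator of the effect on the other, although both arise after randomization and the intervention targets both

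*Protocol*

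**What the plan says.** Section 8.3.3.1 of the protocol, headed as moderation, states that the effect on each main outcome could be modified by the other. It will explore whether "for patients with larger reductions in depressive symptoms, there is a stronger effect of the intervention on days of OUD treatment" than for patients with smaller reductions, and "whether patients with more days of OUD medication treatment show a stronger effect of the intervention on reductions in depressive symptoms" than patients with fewer days.

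The two proposed moderators are the trial's own outcomes:

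- Section 8.3.1: "The primary outcome is a continuous measure of days of OUD treatment with buprenorphine in the 365 days after randomization".
- Section 3.2.2: the depression outcome is the reduction "from the study qualifying PHQ score to follow-up PHQ score documented as part of routine clinical care 3-13 months later".

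Section 3.1 describes an intervention aimed at "engaging patients in medication treatment for OUD and depression, reducing depressive symptoms".

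Elsewhere the protocol keeps these roles apart. Section 3.3.2 ties its subgroups and modifiers to "important subgroups at baseline (defined as up to 2 years before randomization"), and Section 6.6 treats engagement with the nurse care manager, a post-randomization variable, as an exploratory mediator.

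**The concern.** A moderator has to be something that assignment cannot change. PHQ reduction and buprenorphine days can both be changed by assignment, and their measurement windows overlap almost entirely, so neither is fixed before the other. An intervention patient with a large PHQ reduction is not the counterpart of a usual-care patient with the same reduction, since some of the former got there because of the offer. Two problems follow.

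- If the two outcomes are correlated within patients, the arm contrast inside each stratum is biased.
- If benefit runs through engagement, engaged patients collect in the better-response stratum of the intervention arm. The contrast is then larger there without either outcome strengthening the effect on the other.

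The paragraph also does not say whose reduction defines the strata: the one observed, the one a patient would have if offered the program, or the one under usual care. These are different estimands.

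At stake is a secondary claim that depression response strengthens the effect on OUD treatment, or the reverse, when the data show only who engaged. For direction 1 the patient must also have a follow-up PHQ, which Section 8.1.2 expects in 60%.

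**Working it through.** **Inputs from the protocol.** Section 8.1.1: SD 98.3 days, 760 analysed, detectable difference 20 days; "if 35% of patients engage with the intervention, to have 80% power we would need to observe a mean difference of 57.1 days". Section 8.1.2: detectable difference 1.72 points, 4.91 among the engaged at 35%; "These calculations assume a 60% PHQ follow-up rate (among the initial sample of 800 patients) and standard deviation of 6.7 for the outcome", so N = 480.

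**The protocol's figures reproduce.** The detectable difference is (1.960 + 0.842) × SD × √(4/N).

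- Days: 2.802 × 98.3 × √(4/760) = 19.98 (stated 20).
- PHQ: 2.802 × 6.7 × √(4/480) = 1.71 (stated 1.72).
- Among the engaged: 20/0.35 = 57.1 days and 1.72/0.35 = 4.91 points.

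**Assumptions, not in the protocol.** Normal outcomes, observed PHQ reduction split at the pooled median, within-patient correlation r from 0 to 0.5.

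**Formula.** Let component k of an arm have weight w_k, mean PHQ reduction m_k and effect on days d_k. With cut c and z_k = (c − m_k)/6.7, mean days above the cut (relative to the usual-care mean) are

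Σ w_k[(1 − Φ(z_k)) d_k + r × 98.3 × φ(z_k)] / Σ w_k(1 − Φ(z_k)).

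Below the cut, Φ(z_k) replaces 1 − Φ(z_k) and −φ(z_k) replaces φ(z_k).

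**Case 1: 20 days and 1.72 points in every patient.** The cut lies at 0.86, so z = ∓0.128 and φ = 0.3957. Above it are 55.1% of the intervention arm and 44.9% of usual care. The bias factor is 0.3957/0.551 − 0.3957/0.449 = −0.163. At r = 0.3 the bias is −0.163 × 0.3 × 98.3 = −4.8 days, so the stratum effect is 20 − 4.8 = 15.2.

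**Case 2: no effect on days, 4.91 points in the engaged 35%.** Above the cut are 54.9% and 45.1%.

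**Case 3: 57.1 days and 4.91 points in the same 35%.** Engaged patients make up 46.5% of the intervention arm above the cut and 21.0% below it. At r = 0 the contrasts are 57.1 × 0.465 = 26.6 and 57.1 × 0.210 = 12.0.

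Apparent effect on days, larger / smaller PHQ reduction:

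| r | Case 1 (truth 20) | Case 2 (truth 0) | Case 3 |
|---|---|---|---|
| 0 | 20.0 / 20.0 | 0 / 0 | 26.6 / 12.0 |
| 0.1 | 18.4 / 18.4 | -1.9 / -1.0 | 24.6 / 11.0 |
| 0.3 | 15.2 / 15.2 | -5.8 / -3.1 | 20.8 / 8.9 |
| 0.5 | 12.0 / 12.0 | -9.7 / -5.2 | 16.9 / 6.8 |

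In cases 1 and 2 the truth is the same however the strata are defined. A negative r reverses the sign of the bias. Over the protocol's engagement range, case 2 at r = 0.3 gives -6.0 / -2.7 (30% engaged, 5.73 points) and -5.4 / -3.9 (50%, 3.44 points).

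**Reverse direction.** With a normal median split on days, case 1 shows 1.72, 1.63, 1.46 and 1.29 points in both halves at r = 0, 0.1, 0.3 and 0.5. Case 3 shows 2.18 / 1.17 at r = 0 and 1.88 / 0.99 at r = 0.3.

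**Precision.** Simulation at N = 480 gives a standard error of about 12.4 days per half at r = 0.3. The bias in cases 1 and 2 there runs from 3.1/12.4 = 0.25 to 5.8/12.4 = 0.47 standard errors. The interaction test rejects in 4.8% to 6.0% of trials over cases 1 and 2, and in about 12% (r = 0) and 10% (r = 0.3) in case 3.

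**The case against.** The strongest reply is that no procedure is written. Section 8.3.3.1 only proposes to explore a question; it names no model, cut-point or test. The parent Section 8.3.3 leaves the final approach to the SAP, which could define principal strata. This stands in part: the median split is an illustration, and a valid estimand remains open. But the subsection itself defers nothing, and it already fixes the question as moderation by an outcome. Its natural reading is a comparison by observed values.

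A second reply is that the section asks about a difference between strata. In case 1 that difference is zero, which is right, and in case 2 at r = 0.3 it is 2.7 days. Only case 3 gives a sizeable gap, 14.6 days at r = 0, which is still below its standard error of about 18 days. At r = 0 that gap also equals the true effect by PHQ response under the offer. All of this is correct. The case 3 gap misleads only when read as causal modification, which is the reading the section's wording invites. The effects within strata remain biased in cases 1 and 2 whenever r differs from 0.

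A third reply is that days are far from normal: Section 8.1.1 describes peaks at 0 and 365. A beta distribution matched to mean 46.7 and SD 98.3 puts about 60% of usual-care patients below one day, so a median split on days is unrealistic. The reverse-direction point figures should therefore be read as direction only. With a beta outcome, comparing any with no days, the case 3 gap persists and widens (about 2.6 against 0.7 points, with sizes depending on how the effect is built in). The 26.6 and 12.0 days at r = 0 depend only on the engaged shares and the mean effect, not on the shape of the days distribution.

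**Conclusion.** The concern holds. As worded, Section 8.3.3.1 plans a comparison that randomization does not protect, and it calls the result moderation. At an assumed r of 0.3 the stratum effects on days are off by 3.1 to 5.8 days in cases 1 and 2, against detectable differences of 20 days. With engagement-driven benefit, a gap of 26.6 against 12.0 days appears at r = 0 although neither outcome modifies the effect on the other. That mixture is close to the trial's planning scenario, since Section 8.1.1 expects half or more of the intervention arm not to take part.

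The sizes rest on an assumed correlation, normal outcomes and a median split; the principle does not. The consequence is confined to an exploratory analysis. The interaction test stays near its nominal level unless engagement drives both outcomes, and the primary and powered secondary intention-to-treat analyses in Sections 8.2 to 8.3.2 are unaffected. The paragraph should be changed, but nothing confirmatory depends on it.

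**What to change.** Reword Section 8.3.3.1 in two parts.

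1. Limit effect modification to baseline variables, for example treatment by baseline PHQ and treatment by baseline buprenorphine days. Section 3.3.2 already plans baseline OUD medication treatment as a modifier.
2. Baseline interactions do not answer whether OUD and depression responses go together. Put that question either as a between-arm comparison of the joint outcome, or as a mediation or principal-stratum analysis with its estimand and assumptions stated. If the present comparison is kept, report it as a descriptive, non-causal association and drop the word moderation.

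The cost is one reworded paragraph and one alternative exploratory model. No new data are needed and the sample size does not change.
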